4.5. Part C Per-Protocol (PP) Set

The Part C Per-Protocol Set (Part C PPS) consists of all participants who were randomized in Part A, received mRNA-1273 50 ug booster in Part C after primary series per schedule, pre-booster SARS-CoV-2 negative, and have no major protocol deviations that impact critical or key data.

Participants who did not receive the treatment as randomized in Part A, did not receive 2 doses of the primary series of mRNA-1273, or did not receive Dose 2 of mRNA-1273 within [21, 42] days after Dose 1 will be excluded from the Part C Per-Protocol Set.

Part C PPS will be used for analysis of effectiveness of booster.

4.6. Per-Protocol (PP) Primary Series Set

The PP Primary Series Set consists of all participants in Per-Protocol Set who received two doses of mRNA-1273 primary series per schedule in Part A or Part B, with negative pre-Dose 1 SARS-CoV-2 status, and had no major protocol deviations that impact critical or key study data.

Participants who did not receive the treatment as randomized in Part A, did not receive 2 doses of the primary series of mRNA-1273, or did not receive Dose 2 of mRNA-1273 within [21, 42] days after Dose 1 of mRNA-1273 will be excluded from the PP Primary Series Set.

PP Primary Series Set will be used for the effectiveness analysis of the mRNA-1273 primary series. PP Primary Series Set will also be used to assess effectiveness of participants received booster dose and those who did not receive booster dose by pre-booster SARS-CoV-2 status.

4.7. Primary Series Safety Set

The Primary Series Safety Set consists of all participants who were randomized in Part A and received at least one dose of mRNA-1273 primary series. The Primary Series Safety Set will be used for the safety analysis of the mRNA-1273 primary series.

5. Statistical Analysis

5.1. General Considerations

5.1.1. General Considerations, Derivations and Strategy for incomplete/missing data

The Schedule of Events is provided in the protocol Table 16-23.

Continuous variables will be summarized using the following descriptive summary statistics: the number of subjects (n), mean, standard deviation (SD), median, minimum (min), and maximum (max).

Categorical variables will be summarized using counts and percentages.

Age: unless otherwise specified, age is calculated as the age at screening and will be used for derivation of age group.

Study day relative to an injection will be calculated as date of assessment/event – date of the most recent injection prior to the assessment/event + 1, unless otherwise specified.

Unscheduled visits: measurements at Unscheduled visits will be included in analysis as follows:

- In scheduled visit windows per specified visit windowing rules.
- In the derivation of baseline measurements.
- In the derivation of maximum/minimum values after 1st dose and maximum/minimum change from baseline values for safety analyses.
- In individual subject data listings as appropriate.

Visit windowing rules: The analysis visit windows for protocol-defined visits are provided in [Appendix B](#).

Incomplete/missing data:

- Imputation rules for missing dates of prior/concomitant medications, non-study vaccinations and procedures are provided in [Appendix C](#).
- Imputation rules for missing AE dates are provided in [Appendix D](#).
- If the laboratory results are reported as below the LLOQ (e.g. < 0.1), the numeric values will be substituted by $0.5 \times \text{LLOQ}$ in the summary when treating the results as continuous variables. If the laboratory results are reported as greater than the ULOQ (e.g. > 3000) without actual value, the numeric values will be substituted by ULOQ in the summary statistics for continuous variable.
- Other incomplete/missing data will not be imputed, unless specified otherwise.

5.1.2. Baseline (Pre-Dose 1) in Part A, Unblinding/PDV in Part B, Pre-booster in Part C and pre-Vaccination/pre-Dose 1 of mRNA-1273

Baseline (Pre-Dose 1), unless specified otherwise, is defined as the most recent non-missing measurement (scheduled or unscheduled) collected before the first dose in Part A.

For analyses of Part B (OL phase), please also refer to Section 6.1 of SAP Version 2.0.

For analyses of primary series of mRNA-1273 (Part A and Part B), first dose of mRNA-1273, either in Part A for those randomized to mRNA-1273 in Part A, or in Part B for those who were randomized to Placebo in Part A and unblinded and received mRNA-1273 in Part B, will be used as reference of “baseline”, and will be referred to as **Pre-vaccination**, or, **Pre-Dose 1 of mRNA-1273**.

For analyses of booster (Part C), the booster dose of mRNA-1273 in the BD phase will be used as reference for relevant analyses, and will be referred to as **Pre-booster**.

For the summary statistics of all numerical variables unless otherwise specified, the display precision will follow programming standards. Please see [Appendix A](#) for variable display standards.

When count data are presented, the percentage will be suppressed when the count is zero in order to draw attention to the non-zero counts. A row denoted “Missing” will be included in count tabulations where specified on the shells to account for dropouts and missing values.

5.1.3. SARS-CoV-2 status

Baseline SARS-CoV-2 status was the baseline status in Part A, and was determined by virologic and serologic evidence of SARS-CoV-2 infection on or before Day 1 (pre-Dose 1) in Part A, and is defined in SAP Version 2.0.

Positive SARS-CoV-2 status at Baseline in Part A is defined as a positive RT-PCR test for SARS-CoV-2, and/or a positive serology test based on bAb specific to SARS-CoV-2 nucleocapsid (as measured by Roche Elecsys Anti-SARS-CoV-2 assay) on or before Day 1 in Part A.

Negative status at Baseline in Part A is defined as a negative RT-PCR test for SARS-CoV-2 and a negative serology test (as measured by Roche Elecsys Anti-SARS-CoV-2 assay) on or before Day 1 in Part A.

The baseline SARS-CoV-2 status in Part A is defined as missing for subjects with both tests missing, or with one test missing and one test negative.

Subjects with negative Baseline SARS-CoV-2 status will be included in the mITT population; subjects with positive or missing baseline SARS-CoV-2 status will be excluded from the mITT and PP population.

SARS-CoV-2 status at unblinding/PDV is the SARS-CoV-2 status at the start of Part B, determined by virologic and serologic evidence of SARS-CoV-2 infection at unblinding/PDV in Part B.

Positive SARS-CoV-2 status is defined as a positive RT-PCR test for SARS-CoV-2, and/or a positive serology test based on bAb specific to SARS-CoV-2 nucleocapsid (as measured by Roche Elecsys Anti-SARS-CoV-2 assay); negative SARS-CoV-2 status is defined as both negative RT-PCR and negative Elecsys at unblinding/PDV at Part B. If one test is negative and one test is missing, SARS-CoV-2 status would be missing at unblinding /PDV.

Pre-booster SARS-CoV-2 status for Part C, is determined by using virologic and serologic evidence of SARS-CoV-2 infection prior to the booster in Part C.

Positive pre-booster SARS-CoV-2 status is defined as a positive RT-PCR test for SARS-CoV-2, and/or a positive serology test based on bAb specific to SARS-CoV-2 nucleocapsid (as measured by Roche Elecsys Anti-SARS-CoV-2 assay) on or before the date of booster (BD-Day 1).

Negative pre-booster SARS-CoV-2 status is defined as no virologic or serologic evidence of SARS-CoV-2 infection on or before BD-Day 1 (pre-booster), i.e. RT-PCR result is not positive if available at BD-Day 1 and a negative bAb specific to SARS-CoV-2 nucleocapsid (as measured by Roche Elecsys Anti-SARS-CoV-2 assay) on or before BD-Day 1.

The pre-booster SARS-CoV-2 status is defined as missing for subjects with both tests missing, or no Elecsys results on or before BD-Day 1 and RT-PCR not positive at pre-booster (at BD-Day 1). Please note the NP Swab at BD-Day 1 is optional, which is a limitation to detect the infections occurred prior to Part C.

Subjects with positive pre-booster SARS-CoV-2 status will be excluded from the Part C PP Set and Part C PPIS-Neg.

5.1.4. Analysis Strategy and Treatment Groups

Analyses Strategy: The following analyses may be performed by using Part B and Part C data. Please also refer to “Analysis Periods” subsection (Section 5.1.5) in this section. The analysis periods are summarized in Table 1 of Section 5.1.5.

- To assess effectiveness and safety during Part B (OL-phase period), analyses may be conducted using the analysis periods and treatment groups for Efficacy and Safety of Part B based on data collected in Part B.
- To assess the effectiveness and safety after booster (Part C), Part C analyses will be conducted using the analysis periods and treatment groups for Effectiveness and Safety of Part C based on data collected during the booster dose phase (Part C).
- To assess effectiveness of the primary series of mRNA-1273, analyses of effectiveness may be conducted using analysis periods and treatment groups for efficacy using data collected in Part A and Part B. Please note only those who received 2 doses of mRNA-1273 would be included in the analyses.
- To assess effectiveness of a booster, and long term effectiveness (or durability) of mRNA-1273 primary series, analysis of effectiveness may be conducted using analysis periods and treatment groups for efficacy using data collected during the blinded phase (Part A), the open-label phase (Part B), and the booster dose phase (part C).

Treatment cohorts/groups

The following treatment groups have been used in analysis of blinded phase (Part A):

- mRNA-1273
- Placebo

The following treatment groups have been and will be used in analysis of Part B:

- mRNA-1273
- Placebo-mRNA-1273
- Placebo

The above 3 treatment groups may also be used to assess long term effectiveness of mRNA-1273 (Part A and Part B).

If a participant requested to receive mRNA-1273 in Part B (OL phase), the subject will be included to mRNA-1273 cohort as the planned treatment group for efficacy analysis, regardless whether the dose was actually received or not. Participants who were randomized to placebo and planned to receive mRNA-1273 in the open-label phase will be included to the Placebo-mRNA-1273 Cohort for efficacy analysis. Participants who only received placebo in the blinded phase and received mRNA-1273 in the open-label phase will be included in the Placebo-mRNA-1273 Cohort for safety analysis and efficacy analysis for Part B.

The following treatment groups will be used in analysis of Part C:

- Booster 50 µg after mRNA-1273 Primary Series
- Booster 50 µg after Placebo-mRNA-1273 Primary Series

In addition, an overall/total booster group in Part C may be presented in the summaries and analysis of Part C.

The following treatment groups will be used in analyses of mRNA-1273 primary series:

- mRNA-1273
- Placebo-mRNA-1273

All analyses and data summaries/display for efficacy will be provided by corresponding treatment cohorts using appropriate analysis population unless otherwise specified.

5.1.5. Analysis Periods

Analysis periods and treatment groups for analysis of Part B, Part C, and Primary Series are summarized in Table 1. For effectiveness, participants will be included in treatment groups based on ‘as-planned’ or ‘intent-to-treat’ assignments; for safety, participants will be included in treatment groups based on ‘as treated’ groups (treatment actually received), details are provided to Appendix F. For analysis of immunogenicity, ‘per-protocol’ sets will be used as analysis population and ‘per-protocol’ sets require participants receiving planned treatments.

Table 1 Analysis Periods for Analyses of Part B, Part C, and Primary Series

Treatment Group/Cohort	Description	Analysis Period
Part B (Effectiveness)		
mRNA-1273	Participants randomized to mRNA-1273 in the Blinded Phase Date of reference: PDV/unblinding	From PDV/unblinding to earlier date of (BD-1 visit, DBL or data cutoff date for efficacy, last observed in study ^a)
Placebo	Participants randomized to Placebo in the Blinded Phase and did not request to receive mRNA-1273 in Part B Date of reference: Dose 1 of mRNA-1273	
Placebo-mRNA-1273	Participants randomized to Placebo in the Blinded phase and requested to receive mRNA-1273 in Part B Date of reference: Dose 1 of mRNA-1273 in Part B	
Part B (Safety)		
mRNA-1273	Participants received at least one dose of mRNA-1273 in the Blinded Phase	From PDV/unblinding or 1 st dose of mRNA-1273 in Part B to earlier date of (BD- Day 1, DBL or data cutoff date for safety, last observed in study ^a).
Placebo	Participants only received Placebo in the Blinded Phase and did not receive mRNA-1273 in Part B	
Placebo-mRNA-1273	Participants only received Placebo in the Blinded phase and received mRNA-1273 in Part B	
Part C (Effectiveness, Immunogenicity, Safety)		
Booster 50 µg after mRNA-1273 primary series	Participants randomized to/received mRNA-1273 in the Blinded Phase and received booster 50 µg in Part C Date of reference: date of booster	From dose date in Part C to earlier date of (DBL or data cutoff date for safety, last observed in study ^a).

Booster 50 µg after Placebo-mRNA-1273 Primary Series	Participants randomized to /only received Placebo in the Blinded Phase and received at least one dose of mRNA-1273 in Part B and received booster 50 µg in Part C Date of reference: date of booster	
Booster 50 µg	Participants randomized in the blinded phase and received booster 50 µg in Part C Date of reference: date of booster	From dose date in Part C to earlier date of (DBL or data cutoff date for safety, last observed in study ^a).
Not received booster	Participants randomized to/received mRNA-1273 in Part A or B and did not receive booster in Part C Date of reference: date of BD-visit 1	Up to earlier date of (DBL or data cutoff date for safety, last observed in study ^a).
Placebo	Participants randomized to/only received Placebo in Part A or B and did not receive booster in Part C Date of reference: date of BD-visit 1	From BD-visit 1 in Part C to earlier date of (DBL or data cutoff date for safety, last observed in study ^a).
Effectiveness, Immunogenicity of mRNA-1273 primary Series		
mRNA-1273	Participants randomized to mRNA-1273 in the Blinded Phase	From Dose 1 of mRNA-1273 to earlier date of (booster date, DBL or data cutoff date, last observed in study ^a).
Placebo-mRNA-1273	Participants randomized to Placebo and received mRNA-1273 in Part B	
Safety of mRNA-1273 primary Series		
mRNA-1273	Participants received mRNA-1273 in the Blinded Phase	From Dose 1 of mRNA-1273 to earlier date of (booster date, DBL or data cutoff date, last observed in study ^a).
Placebo-mRNA-1273	Participants received Placebo in the Blinded phase and received mRNA-1273 in Part B	

^a last observed in study is the earliest date of study discontinuation, study completion, or death.

All analyses will be conducted using SAS Version 9.4 or higher unless otherwise specified.

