Participants who are unblinded, received placebo, are eligible, and request to receive mRNA-1273 (as long as investigational vaccine is available) (Figure 2), will have the following clinic visits as shown in the Supplemental SoE (Table 21):

- Open-label Dose 1 (OL-D1): To occur at the PDV or at a scheduled subsequent visit.
- Open-label Dose 2 (OL-D29): To occur 28 days after Dose 1 on OL-D1.
- Open-label Clinic Visit (OL-D57): To occur 1 month after Dose 2 on OL-D29.

- And in addition, continue to comply with the Original Study SoEs ([Table 16](#), [Table 17](#), [Table 18](#), and [Table 19](#)) as applicable.
- Participants who are unblinded, and received ONLY 1 dose of mRNA-1273 may be eligible to receive 1 more dose of mRNA-1273 if: They had a dosing error in Part A of the study that resulted in 1 dose of mRNA-1273 and 1 dose of placebo being administered.
- They did not have an AE that contraindicated the second dose of mRNA-1273 in Part A of the study.
- They did not withdraw consent in Part A of the study.
- They did not complete their second dose in Part A of the study for reasons other than the above.

If participants are eligible, and request to receive mRNA-1273 ([Figure 2](#)) will proceed to have the following clinic visits as shown in the Modified Supplemental SoEs ([Table 22](#)):

- Their second dose on OL-D1: To occur at the PDV or at a scheduled subsequent visit.
- Open-label Clinic Visit (OL-D29): To occur 1 month after Dose 2 on OL-D1.
- And in addition, continue to comply with the Original Study SoEs ([Table 16](#), [Table 17](#), [Table 18](#), and [Table 19](#)) as applicable.

All participants remain on their original SoE to complete 24 months of follow-up after Dose 2; study participants who enter the Supplemental/Modified Supplemental SoE as described above do so in addition to their original SoE. Accordingly, all study participants will complete the full study follow-up to 24 months after the second dose of their original inoculation (mRNA-1273 or placebo) or 25 months after the first dose if the second dose is missed.

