9.5.1.3. Long-term Efficacy Analysis

Long-term efficacy of the primary vaccination series with mRNA-1273 will be evaluated after the primary analysis by including data collected in the Open-Label Observational Phase (Part B). Long-term efficacy data will be summarized descriptively by treatment cohort described in [Table 10](#) without cohort comparison. The long-term efficacy endpoints are listed in

[Table 11](#) with the same case definitions specified in [Table 1](#). In the primary approach, cases will be counted starting 14 days after the second dose of IP for participants in treatment cohorts of mRNA-1273 and placebo or starting 14 days after the second dose of mRNA-1273 for participants in the Placebo-mRNA-1273 Cohort. Sensitivity analyses with cases starting from the second dose, 14 days after the first dose, or first dose of IP for participants in the cohorts of mRNA-1273 and placebo, or mRNA-1273 for participants in the Placebo-mRNA-1273 Cohort may be provided. Incidences of cases assessed by numbers, rates, and 2-sided 95% CI based on the exact method adjusting for person-time will be summarized by treatment cohort. The Kaplan-Meier analysis will be used to estimate cumulative incidences of time to first cases by treatment cohort. Long-term efficacy analysis will be performed using the PP Set and mITT Set.

Efficacy analyses of unblinded/open-label phase data collected in Part B will be provided, as measured by the incidence rate of COVID-19 after the BD of mRNA-1273. The details of analysis of long-term efficacy and open-label phase data (Part B and Part C) will be provided in the SAP.

Table 10: Treatment Cohorts for the Long-term Efficacy Analyses

Treatment Cohort	Description
mRNA-1273	Participants randomized to mRNA-1273 in the Blinded Phase.
Placebo	Participants randomized to Placebo in the Blinded Phase and did not crossover to mRNA-1273 in the Open-Label Observational Phase.
Placebo-mRNA-1273	Participants randomized to Placebo in the Blinded Phase and crossed over to mRNA-1273 in the Open-Label Observational Phase.

Table 11: Long-term Efficacy Endpoints

Long-term Efficacy Endpoint

Cases of COVID-19 starting 14 days after the second injection of:
 
 • IP for participants in the mRNA-1273 Cohort and the Placebo Cohort, 
or
 
 • mRNA-1273 for participants in the Placebo-mRNA-1273 Cohort.

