Considering Part B/unblinded phase of the study, the following analysis periods may be used. SAP Part B will provide more details, and if the definition for Part B in SAP Part B differs from that described in this SAP, SAP Part B will prevail.

The following analysis period and treatment groups for Efficacy of the unblinded phase (Part B) may be used:

Part B Cohort	Description	Part B Analysis Period for Efficacy
mRNA-1273	Participants randomized to mRNA-1273 in the Blinded Phase	From PDV/unblinding to earlier date (data cutoff date for efficacy, last observed in Study) where last observed is earlier of (study discontinuation, study completion, death)
Placebo	Participants randomized to Placebo in the Blinded Phase and did not receive mRNA-1273 in Part B	
Placebo-mRNA-1273	Participants randomized to Placebo in the Blinded phase and received mRNA-1273 in Part B	

The following analysis period of the unblinded phase (Part B) and treatment groups for Safety analysis of the unblinded phase (Part B) may be used:

Part B Cohort	Description	Part B Analysis Period for Safety
mRNA-1273	Participants received at least one dose of mRNA-1273 in the Blinded Phase	From PDV/unblinding to earlier date of (data cutoff date for safety, last observed in Study). If a participant received mRNA-1273 in Part B, from 1 st date of study IP in Part B to earlier date of (data cutoff date for safety, last observed in Study).
Placebo	Participants only received Placebo in the Blinded Phase and did not receive mRNA-1273 in Part B	From PDV/unblinding to earlier date of (data cutoff date for safety, last observed in Study)
Placebo-mRNA-1273	Participants only received Placebo in the Blinded phase and received mRNA-1273 in Part B	From first dose of mRNA-1273 in Part B to earlier date of (data cutoff date for safety, last observed in Study)

All analyses will be conducted using SAS Version 9.4 or higher unless otherwise specified.

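### The Part B effectiveness analysis places placebo participants in the Placebo-mRNA-1273 cohort by request rather than by receipt, and Table 1 does not settle when that cohort's time starts

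*SAP*

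**What the plan says.** Table 1 of the Parts B and C SAP (Section 5.1.5) groups participants for effectiveness as planned and describes the switch cohort as "Participants randomized to Placebo in the Blinded phase and requested to receive mRNA-1273 in Part B". The analysis period printed for the Part B effectiveness block is "From PDV/unblinding to earlier date of (BD-1 visit, DBL or data cutoff date for efficacy" or last observation in the study. The same table gives Placebo-mRNA-1273 a reference date of Dose 1 in Part B. It gives the Placebo cohort, who did not request vaccine, a reference date of Dose 1 of mRNA-1273.

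Section 5.1.4 says that a participant who asks for vaccine in Part B is "included to mRNA-1273 cohort as the planned treatment group for efficacy analysis, regardless whether the dose was actually received or not". The next sentence says that placebo participants who "planned to receive mRNA-1273 in the open-label phase will be included to the Placebo-mRNA-1273 Cohort for efficacy analysis". Appendix F (treatment cohorts) lists the placebo participant who requested vaccine but has no Part B dose: Placebo-mRNA-1273 for efficacy, Placebo for safety.

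The other two definitions differ. Protocol Table 10 (Section 9.5.1.3) has "Participants randomized to Placebo in the Blinded Phase and crossed over to mRNA-1273 in the Open-Label Observational Phase". The Part A SAP (Section 6.1, Part B efficacy) has "Participants randomized to Placebo in the Blinded phase and received mRNA-1273 in Part B". Section 6 of the Parts B and C SAP, on changes from the protocol, reads as not applicable.

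**The concern.** Crossover was chosen, not randomised, so an as-planned label does not preserve a randomised comparison here. What the label does is put people who were never vaccinated into a cohort named for vaccination.

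The timing matters as well. Protocol Section 4.1.2 allows a gap before the first open-label dose: "Open-label Dose 1 (OL-D1): To occur at the PDV or at a scheduled subsequent visit". Dosing also depends on eligibility and supply. Under Protocol Section 7.1, symptomatic COVID-19 at the time scheduled for Part B dosing can delay dosing or lead to its discontinuation. Requesters who become cases before dosing may therefore be among those dosed late or not at all, and still be counted in Placebo-mRNA-1273.

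At stake is the Part B incidence rate reported for newly vaccinated participants. Two programmers working from this text could derive different rates.

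**Working it through.** **1. Who is in the cohort**

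| Source | Membership of Placebo-mRNA-1273 |
|---|---|
| Protocol Table 10 | Crossed over |
| Part A SAP, Section 6.1 | Received mRNA-1273 in Part B |
| Parts B and C SAP, Table 1 (effectiveness) | Requested |
| Parts B and C SAP, Appendix F (efficacy) | Requested, dosed or not |

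The request rule is the operative one. The Parts B and C SAP prevails over the protocol (its Section 1) and over the Part A SAP on Part B definitions (Part A SAP, Section 6.1). The analysis population does not remove undosed requesters: Part B uses the PP Set (Sections 5.3 and 5.3.1.2.1), which rests on Part A dosing and requires no open-label dose.

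**2. When time starts**

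The printed period starts at PDV/unblinding. It appears once and is probably a merged cell covering all three cohorts; the Part A SAP, which also starts at PDV/unblinding, supports that reading. Section 5.3.1.2.1 sets at-risk status at PDV/unblinding too. The Part B safety period adds first dose in Part B as an alternative start; the effectiveness period does not. Against this stands the Dose 1 reference date in the Placebo-mRNA-1273 row. If the period governs, time from PDV to open-label Dose 1 (OL-D1) counts as Placebo-mRNA-1273. If the reference date governs, that gap drops out, but never-dosed requesters have no reference date and no rule covers them.

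**3. Size, as an illustration**

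The plan gives no figure to reproduce. Inputs from the documents:
- Lag to full effect of 42 days (28 + 14; Parts B and C SAP, Section 5.6.1.1).
- Efficacy (VE) of 60% (Protocol Section 9.3) and 94.5% (Parts B and C SAP, Section 1).

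Assumed, because the documents do not give them:
- q, the never-dosed share of requesters: 0 to 5%.
- g, the gap from PDV to OL-D1: 0 to 30 days.
- F, follow-up after Dose 1: 150 to 240 days.

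Take the hazard as 1 while unprotected and 1 − VE from day 42 after Dose 1.

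- As written, with the period governing: {q(F+g) + (1−q)[g + 42 + (F−42)(1−VE)]} / (F+g)
- By receipt, from Dose 1: [42 + (F−42)(1−VE)] / F

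Example with VE 94.5%, F 240, q 2%, g 14:
- By receipt: (42 + 198 × 0.055)/240 = 52.89/240 = 0.220.
- As written: (0.02 × 254 + 0.98 × 66.89)/254 = 70.63/254 = 0.278.
- Ratio: 1.26.

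Ratio of the as-written rate to the by-receipt rate, ranges over F = 150 and 240:

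| q | g (days) | VE 60% | VE 94.5% |
|---|---|---|---|
| 0 | 0 | 1.00 | 1.00 |
| 0 | 14 | 1.05–1.06 | 1.18–1.19 |
| 0 | 30 | 1.11–1.13 | 1.35–1.39 |
| 2% | 0 | 1.02 | 1.04–1.07 |
| 2% | 14 | 1.07–1.08 | 1.22–1.26 |
| 2% | 30 | 1.13–1.14 | 1.39–1.46 |
| 5% | 0 | 1.04–1.05 | 1.11–1.18 |
| 5% | 14 | 1.10 | 1.28–1.36 |
| 5% | 30 | 1.15–1.16 | 1.44–1.55 |

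The g = 0 rows show the effect of undosed requesters alone. The model does not allow for cases themselves delaying or preventing dosing.

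**The case against.** The case for leaving the text alone has real content.

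- **Dose-anchored handling exists.** Part B is to follow an approach similar to the primary-series one, which splits time at Dose 1, Dose 2 and 14 days after Dose 2. Protocol Section 9.5.1.3 counts this cohort's cases from 14 days after the second mRNA-1273 dose. Section 5.3.1.2 describes a dynamic at-risk approach, with the booster only as an example. This stands in part: a careful programmer could drop pre-dose time. None of it says where never-dosed requesters go, and it sits beside fixed as-planned cohorts.
- **Section 5.1.4 has a receipt sentence too.** It places placebo participants who received mRNA-1273 in Placebo-mRNA-1273 for safety and Part B efficacy. That includes recipients; it does not exclude undosed requesters, whom Appendix F expressly includes.
- **The sentence on requesters can be read narrowly.** The rule that applies "regardless whether the dose was actually received or not" may be meant for participants randomised to mRNA-1273 who ask for a further dose. Appendix F keeps them in mRNA-1273 either way. This stands, so the sentence needs limiting, not deleting. The point does not depend on it, because Table 1 and Appendix F carry the request rule.
- **The undosed time may be small.** Protocol Table 21 allows the PDV and OL-D1 on the same day, and placebo participants who intend to take an outside vaccine are withdrawn. This stands; q and g could be near zero.
- **The consequence is limited.** The protocol plans long-term efficacy descriptively, without cohort comparison. The primary-series and relative-effectiveness analyses use recipients of two doses from Dose 1. This stands.

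**Conclusion.** The text needs correcting. Request-based membership is an unrecorded departure from Protocol Table 10, the Placebo reference date is unusable, and the period and reference date for Placebo-mRNA-1273 conflict. Followed as written, the plan biases that cohort's Part B rate upward, against the vaccine. The inflation is about 0 to 16% at 60% efficacy and 0 to 55% at 94.5%, conditional on the assumed q, g and F and the 42-day lag. It is zero if every requester was dosed at the PDV. The effect is confined to the descriptive Part B rates.

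Three stronger readings are tempting but not supported:

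- A reader might infer that Table 1 runs this cohort's clock from the PDV alone. The same row gives a Dose 1 reference date, so this is an unresolved conflict.
- A reader might infer that unvaccinated cases are credited to the randomised mRNA-1273 arm. Table 1 and Appendix F keep placebo requesters in a separate cohort.
- A reader might take the 93% efficacy in Protocol Section 2.2.2 and conclude that 5% undosed time inflates the rate by 66% (0.07 × 0.95 + 0.05 = 0.1165; 0.1165/0.07 = 1.66) and cuts efficacy against placebo to 88.4%. That assumes full protection from OL-D1, contrary to the SAP's own six-week lag. It also uses an undosed share the documents do not give, and a contrast with placebo that the protocol does not plan.

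**What to change.** In the Parts B and C SAP, Section 5.1.4, Table 1 and Appendix F:

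- Define the Part B effectiveness cohorts by receipt, as Protocol Table 10 does.
- Count a placebo participant's time from PDV/unblinding to OL-D1 in Placebo, and time from OL-D1 in Placebo-mRNA-1273. Keep all time of undosed requesters in Placebo.
- Set the Placebo reference date to PDV/unblinding, and make the Placebo-mRNA-1273 period agree with its Dose 1 reference date.
- Limit the Section 5.1.4 sentence on the mRNA-1273 cohort to participants randomised to mRNA-1273.
- Record in Section 6 any departure from Protocol Table 10 that is kept.

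The cost is SAP wording and a revised cohort derivation. No new data are needed, because dose dates are already recorded in the eCRF (Protocol Section 6.3).
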